Changes in dietary composition and diversity were considered the main drivers of the shifts in gut bacteria profile. In this multi-disciplinary research study, we will investigate the gut microbiota composition in people with Alzheimer's dementia with challenging behaviours, test the feasibility of recruitment, and provide initial data to support a future grant application involving a dietary intervention study in patients with Alzheimer's disease.

We will test our hypothesis that the gut-brain axis promotes behavioural changes in Alzheimer's dementia and is responsive to changes in gut microbiota profile, by comparing the gut microbiota profile between three participant groups (1) Alzheimer's dementia with challenging behaviour, (2) Alzheimer's dementia without challenging behaviour, and (3) a control group of healthy age-matched elderly. We will also carry out a survey to care homes to assess their willingness to participate in dietary supplementation study.

1. Introduction

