1.1. Rationale for Study

Hypothesis: The composition and/or diversity of the gut microbiota is different between healthy elderly and those with Alzheimer's dementia, who do or do not exhibit behaviour(s) that are challenging

The concept that inspires Ageing-GB is that our gut microbiota impact upon the gut-brain axis and thereby on behaviour. We need to understand the nature of that impact, the underlying mechanisms, and how changes in diet can reprogram our gut microbiota-brain axis to resolve or reduce clinical symptoms associated with Alzheimer's dementia.

However, there has been no published work that we are aware of to examine the gut microbiota profile in patients with Alzheimer's disease. Consequently, first we need to demonstrate the differences in microbiota profile between AD patients with or without behaviours that are more challenging to manage. We believe that our work will be fundamental to provide evidence to support dietary modification or supplementation as cost-effective and safe avenues for alleviating signs and symptoms of dementia in this vulnerable group and thus reduce the carer burden.

This study will require the co-operation of care home managers and staff, and will thus simultaneously assess the feasibility of performing a nutritional intervention study in this group of individuals, in this setting.

2. Study Objectives and Outcomes

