2.1. Objectives

2.1.1. Primary Objective

To compare the composition and activity of the gut microbiota in three groups of elderly individuals: (i) Alzheimer's dementia and challenging behavioural symptoms, (ii) Alzheimer's dementia and no challenging behavioural symptoms, (iii) and people without dementia of any type.

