3.1. Study Description

An observational case-controlled study with three groups of participants with 1:1:1 will be carried out. A total of 60 volunteers, 20 in each group from the following groups (i) Alzheimer's dementia and challenging behavioural symptoms, (ii) Alzheimer's dementia and no challenging behavioural symptoms, (iii) without any type of dementia, will be recruited from care homes.

Each volunteer (assisted by staff) will provide two faecal samples, at least a week apart which will be analysed for microbial composition and activity by assessing Short Chain Fatty Acid profile (SCFA profile). Faecal samples will be collected using a pot on a toilet/commode, which will be sealed and processed in the laboratory within 12hr.

Additional information on regular diet composition will be collected by accessing the weekly care home menu. Staff will observe participants and record every episode which requires staff intervention as a result of behaviours that are challenging to manage.

A quality of life questionnaire will be completed by each volunteer in Alzheimer's dementia groups using DEMQOL (Dementia Quality of Life questionnaire).

DEMQOL is widely used patient reported outcome measures (PROMs) of health related quality of life in people with dementia.

Finally, we will collect other information on medication, personal characteristics, co-morbidities etc. to mitigate any confounding effects.

To achieve the secondary objectives the following outcomes will be assessed.

We will collect information on the following key aspects of feasibility of a larger study (future clinical trial) based on the main hypothesis driven work carried out under aim 3 described below

- (1) Proportion of eligible older people with Alzheimer's dementia with or without challenging behaviours
- (2) Proportion of eligible participants willing to participate
- (3) Proportion of participants who are able provide samples in each group
- (4) Proportion of participants (staff who are looking after them or relatives) who are able to provide study data /information

We will assess participants, their carers and whenever relevant managers and staff of care home and relatives/family members and people with Alzheimer's dementia with regard to willingness to participate in a research trial and to identify issues to be addressed to gain support for such an intervention trial through end of study questionnaire conducted by the study research nurse face to face.

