4.1. Number of Participants

- (i) with Alzheimer's dementia and challenging behavioural symptoms (n=20)
- (ii) with Alzheimer's dementia and no challenging behavioural symptoms (n=20)
- (iii) with no dementia (n=20)

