4.2. Inclusion Criteria

Resident in a care home

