5.3. Screening for Eligibility

In order to be recruited into study group (i) or (ii) there has to be an existing medical diagnosis of Alzheimer's dementia that will be confirmed by cross-referencing with medical records. Likewise for recruitment to group (iii) no such diagnosis should exist. The sub-group stratification of Alzheimer's dementia patients with or without behaviours that are challenging will be ascribed after speaking to care home staff and analysing care home records of participants.

Eligibility will be determined based on the knowledge of care home manager and staff. At this stage, the research team will not have any knowledge of who they are. Potentially eligible participants will first be approached by care home manager/staff to enquire whether they would be willing to speak to research team. Only those who are willing to speak to research team will be approached by the research nurse and provide study information. If they are interested and provide permission to check the eligibility, the diagnosis will be checked against their care home records. In case if the care home staff deem the potential participant lacks capacity, formal capacity assessment will be carried out by medically trained research team member.

Initial screening for eligibility will be carried out by care home staff and second level screening by study team will only happen after the participant has provided informed verbal consent prior to participation. If eligible written informed consent will be taken for study procedures.

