5.4. Ineligible and Non-Recruited Participants

Only eligible volunteers will be recruited to the study, up to the required number in each group. Once this number is reached, any additional interested volunteers will be thanked for their interest. No data will be collected prior to recruitment.

6. Withdrawal Procedures

If any participant wishes to withdraw from the study at any point after recruitment, all data and samples collected will be destroyed. If the carer perceives that participation in the study is causing distress to the volunteer, they will provide advice but if the distress persists the volunteer may be withdrawn from the study. In both cases a 'withdrawn from study' form will be completed and attached to the CRF. Unless such a form is completed (by either the volunteer or their representative) and consent is thus withdrawn, all samples will be kept following appropriate study guidelines. As the study requires 20 participant in each arm of the study, we will replace the withdrawal with further recruitment.

7. Data Collection and Management

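### The summary and hypothesis call the controls healthy and age-matched, but the design recruits care-home residents without dementia, with no matching, no general health criterion and no planned adjustment

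*Combined protocol and SAP*

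**What the plan says.** The comparator is described in two ways.

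- **Summary, before section 1:** group 3 is "a control group of healthy age-matched elderly".
- **Rationale for Study, hypothesis:** the microbiota is "different between healthy elderly and those with Alzheimer's dementia".
- **Section 2.1.1, primary objective:** the third group is described as "and people without dementia of any type".
- **Section 3.1:** group (iii) is "without any type of dementia, will be recruited from care homes". Section 4.1 also defines it only by the absence of dementia, with 20 places.
- **Section 4.2:** the sole inclusion criterion is "Resident in a care home".
- **Section 4.3:** the exclusions, common to all groups, are antibiotics in the previous 8 weeks, active gastrointestinal disease and inability to consent.
- **Section 5.3:** a control must have no existing diagnosis. The staff-and-records check on behaviour is described for the Alzheimer's groups.
- **Section 5.4:** "Only eligible volunteers will be recruited to the study, up to the required number in each group".

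On confounding, section 3.1 says that medication, personal characteristics and co-morbidities will be collected to reduce it. The study matrix in 3.2 schedules demographics, height, weight, co-morbidities, medications, a nutritional assessment and the food menu. Section 9.2 plans descriptive presentation and parametric or non-parametric comparisons among the three groups.

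**The concern.** The words healthy and age-matched each tell a reader that a rival explanation has been dealt with by design. Nothing in sections 4 or 5 does so. The primary objective does use the word elderly, but no age limit is defined. A resident without dementia may be in care for some other serious illness, and may be much younger or older than the residents with Alzheimer's dementia.

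If the groups differ in age, illness or medication, an unadjusted difference in microbiota or SCFA between either Alzheimer's group and the controls could be reported as an effect of dementia. The background section gives reason to take this seriously. It reports that institutionalised older adults have fewer SCFA-production genes and raised inflammatory markers, and it cites a study whose title concerns a microbiota ratio that changes with age. The data are also meant to support a further grant application, so a mislabelled comparator would carry forward.

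**Working it through.** The point is mainly a comparison of texts, so each stated property is taken in turn.

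1. **Age-matched.** The term appears once, in the summary. Sections 4.1 to 4.3, 5.3 and 5.4 give no age range, matching variable, band or quota. The 1:1:1 in section 3.1 fixes group sizes (20, 20, 20), not ages. Section 5.4 stops recruitment by number alone. The property is claimed but no step produces it.

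2. **Healthy.** The term appears in the summary and hypothesis. Two of the three exclusions in 4.3 bear directly on the gut, but all three apply equally to every group, so they do not make the controls healthy in general.

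3. **Without dementia.** This is the definition in 2.1.1, 3.1 and 4.1, and it is what is recruited, with one loose end. In 5.3 the diagnosis that controls must not have is, read literally, Alzheimer's dementia, which is narrower than dementia of any type.

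4. **Analysis.** Sections 3.1 and 3.2 collect the likely confounders. Section 9.2 names no covariate, stratification or matched analysis. The data for adjustment would exist, but no planned use is stated.

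5. **Reach.** Of the three pairwise contrasts, two use group (iii), and these set 20 + 20 = 40 Alzheimer's participants against 20 controls. The third contrast, with against without challenging behaviour, uses no controls. It is the one that the Rationale says must be shown first.

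**Illustration of size.** Section 9.1 claims at least 90% power with 20 volunteers for a 20% shift in SCFA. That figure cannot be reproduced, because no SD, alpha, sidedness or test is given. I assume an unpaired two-group comparison and two-sided alpha of 0.05, and solve for the SD that gives exactly 90% power:

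- SD = δ√(n/2) / (z for alpha + z for power) = 0.20 × √10 / (1.960 + 1.282) = 0.195 of the mean.
- Other assumptions give 0.172 (Bonferroni for three pairs, two-sided) to 0.216 (one-sided 0.05).
- Standard error of a difference = 0.195 × √(2/20) = 0.0617.

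Suppose there is no disease effect, but an age or health imbalance shifts the SCFA mean by b. The chance of a significant unadjusted result is 1 − Φ(1.96 − b/SE) + Φ(−1.96 − b/SE):

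| Assumed shift b | b/SE | Chance of significance |
|---|---|---|
| 5% | 0.81 | about 13% |
| 10% | 1.62 | about 37% |
| 15% | 2.43 | about 68% |

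The shifts are assumptions; the documents give none. Section 9.1 refers to volunteers on a controlled diet. If the SD here is larger, these chances fall, and so does the power for a true effect.

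**The case against.** **The comparison is the one intended.** A reader might infer that the study fails to deliver its stated comparison. The documents do not support that. The primary objective, the design section and the participant numbers agree on people without dementia, and that is what is recruited. The conflict lies between the summary and hypothesis on one side and the governing sections on the other. This objection stands, and it lowers the severity.

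**Care-home controls are a reasonable choice.** A reader might infer from the background on institutionalised adults that these controls are unsuitable. The same passage cuts the other way: if institutional living alters the microbiota, drawing all three groups from care homes holds the type of setting constant. This also stands. The background shows that the label is wrong, not that the comparator is.

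**Confounders are measured.** Age should fall under demographics or personal characteristics, and illness and medication are recorded. It is therefore too strong to say that an imbalance would be read as a dementia effect. It could be, because section 9.2 does not say that these data will be used. The objection stands only in part.

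**Challenging behaviour among controls.** Since "The sub-group stratification of Alzheimer's dementia patients with or without behaviours that are challenging will be ascribed after speaking to care home staff", a reader might infer that controls with such behaviour enter unnoticed and should be excluded. However, section 3.1 has staff record behavioural episodes for participants, and the matrix lists the behavioural chart without restriction, whereas DEMQOL is marked for the Alzheimer's groups only. No objective requires controls to be free of such behaviour, so excluding them would add an eligibility rule that the study does not need.

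**No bias is demonstrated.** This is true. The percentages above show vulnerability under assumed shifts; they are not an estimate.

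**Conclusion.** The inconsistency is certain from the text: two properties claimed for the controls are produced by no selection step, and no adjustment is named that would make up for it. It bears on both Alzheimer's-versus-control contrasts and leaves the contrast between the two Alzheimer's groups untouched. The size of any bias is unknown, because it depends on age and illness differences that the documents do not give.

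This should be fixed. It is not a fatal flaw in a 60-person observational study meant to provide initial data: the primary objective is already worded correctly, the choice of setting is defensible, and the data needed for adjustment are already to be collected.

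**What to change.** - **Summary and hypothesis:** describe group (iii) as care-home residents without dementia, and limit conclusions to that comparator. Align the wording in 5.3 with dementia of any type. Cost: wording only, and a narrower claim.
- **Age matching:** either drop the term, or deliver it in 5.3 and 5.4 by frequency-matching group (iii) to groups (i) and (ii) by broad age band as places fill. Cost: a quota sheet for the research nurse, some willing controls deferred, and possibly slower recruitment. This choice must be made before enrolment, since matching cannot be added afterwards.
- **Section 9.2:** prespecify a sparse adjustment, at least for age, with one summary value per participant. A three-group comparison of 60 people leaves 60 − 3 = 57 residual degrees of freedom, and a linear age term leaves 56. Each further covariate, such as a co-morbidity or medication term, costs at least one more, so keep the list short. Adjustment helps only where the groups' ages overlap, so tabulate age, co-morbidity and medication by group.
- **Behaviour:** report the behavioural chart for group (iii) alongside the other groups, with no new exclusion. Cost: one extra row in a table.

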1.1. Background

Healthy life expectancy is a key area of research. It has been estimated that 36 million people have dementia worldwide (Prince et al., 2013) and that there are 4.6 million new cases of dementia every year (Ferri et al., 2005). Epidemiological evidence supports the hypothesis that modifiable lifestyle-related factors are associated with cognitive decline, opening new avenues for prevention (Solfrizzi et al., 2008). Alzheimer's disease is the commonest cause of dementia in older people, accounting for 60–70% of all dementia cases when using traditional diagnostic criteria for dementia subtypes (Blennow et al., 2006; Fratiglioni et al., 1999).

There are no available cures for AD, but an alternative approach is to use strategies that delay disease progression at an early stage (Lobo et al, 2000). Optimal brain function results from highly complex interactions between numerous genetic and environmental factors, including food intake, physical activity, age and stress (Solfrizzi et al, 2008). Diet in particular has become the object of intense research in relation to cognitive aging and neurodegenerative diseases.

The gut microbiota is a large, diverse collection of microbes, collectively containing 100 times more genes than the host. It is host-specific, contains heritable components, can be modified by diet, surgery or antibiotics, and in its absence nearly all aspects of host physiology are affected (Marchesi et al, 2016). We now realise that the human microbiota is a previously overlooked system that makes a significant contribution to human biology and development. There is a new and exciting field of research with limited published data in the elderly (Mariat et al, 2009; Claesson et al, 2012), that could provide a basis for the design of novel, microbiota-targeted, therapies to improve care of older people who suffer from Alzheimer's dementia.

There is increasing evidence that identifies the gut microbiota as a key conduit between nutrition and brain function (Goyal et al., 2015). Reduction in the frequency of genes encoding short chain fatty acid (SCFA) production was prominent among institutionalized older adults, as were increases in circulating pro-inflammatory cytokines tumour necrosis factor-alpha, interleukins-6 and -8, and C-reactive protein (Claesson et al., 2012).

1.1. Rationale for Study

Hypothesis: The composition and/or diversity of the gut microbiota is different between healthy elderly and those with Alzheimer's dementia, who do or do not exhibit behaviour(s) that are challenging

The concept that inspires Ageing-GB is that our gut microbiota impact upon the gut-brain axis and thereby on behaviour. We need to understand the nature of that impact, the underlying mechanisms, and how changes in diet can reprogram our gut microbiota-brain axis to resolve or reduce clinical symptoms associated with Alzheimer's dementia.

However, there has been no published work that we are aware of to examine the gut microbiota profile in patients with Alzheimer's disease. Consequently, first we need to demonstrate the differences in microbiota profile between AD patients with or without behaviours that are more challenging to manage. We believe that our work will be fundamental to provide evidence to support dietary modification or supplementation as cost-effective and safe avenues for alleviating signs and symptoms of dementia in this vulnerable group and thus reduce the carer burden.

This study will require the co-operation of care home managers and staff, and will thus simultaneously assess the feasibility of performing a nutritional intervention study in this group of individuals, in this setting.

2. Study Objectives and Outcomes

2.1. Objectives

2.1.1. Primary Objective

To compare the composition and activity of the gut microbiota in three groups of elderly individuals: (i) Alzheimer's dementia and challenging behavioural symptoms, (ii) Alzheimer's dementia and no challenging behavioural symptoms, (iii) and people without dementia of any type.

2.1.2. Secondary Objective

To assess the willingness of care homes and carers to participate in a research trial investigating the links between diet and Alzheimer's dementia.

2.2. Outcomes

2.2.1. Primary Outcome

Differences in the composition and activity of gut microbiota between three groups.

2.2.2. Secondary Outcome

The feasibility of undertaking a study with this group of elderly, vulnerable people in a care home setting including assessing the feasibility of the outcome of the future trial such as quality of life outcome.

3. Study Design

3.1. Study Description

An observational case-controlled study with three groups of participants with 1:1:1 will be carried out. A total of 60 volunteers, 20 in each group from the following groups (i) Alzheimer's dementia and challenging behavioural symptoms, (ii) Alzheimer's dementia and no challenging behavioural symptoms, (iii) without any type of dementia, will be recruited from care homes.

Each volunteer (assisted by staff) will provide two faecal samples, at least a week apart which will be analysed for microbial composition and activity by assessing Short Chain Fatty Acid profile (SCFA profile). Faecal samples will be collected using a pot on a toilet/commode, which will be sealed and processed in the laboratory within 12hr.

Additional information on regular diet composition will be collected by accessing the weekly care home menu. Staff will observe participants and record every episode which requires staff intervention as a result of behaviours that are challenging to manage.

A quality of life questionnaire will be completed by each volunteer in Alzheimer's dementia groups using DEMQOL (Dementia Quality of Life questionnaire).

DEMQOL is widely used patient reported outcome measures (PROMs) of health related quality of life in people with dementia.

Finally, we will collect other information on medication, personal characteristics, co-morbidities etc. to mitigate any confounding effects.

To achieve the secondary objectives the following outcomes will be assessed.

We will collect information on the following key aspects of feasibility of a larger study (future clinical trial) based on the main hypothesis driven work carried out under aim 3 described below

- (1) Proportion of eligible older people with Alzheimer's dementia with or without challenging behaviours
- (2) Proportion of eligible participants willing to participate
- (3) Proportion of participants who are able provide samples in each group
- (4) Proportion of participants (staff who are looking after them or relatives) who are able to provide study data /information

We will assess participants, their carers and whenever relevant managers and staff of care home and relatives/family members and people with Alzheimer's dementia with regard to willingness to participate in a research trial and to identify issues to be addressed to gain support for such an intervention trial through end of study questionnaire conducted by the study research nurse face to face.

This will explore the practical issues which need to be considered in the future study. A study completion questionnaire will be introduced after sampling is complete (Appendix B).

